5.1.3. Reporting for the Duke Foundation

- Count/frequency of patients presenting to an ED that have a telepsychiatric consult during the intervention
- Count/frequency of patients with an admission after telepsychiatric consult in the intervention arm
- Count/frequency of patients enrolled in the BH-VPN program
- Count/frequency of patients enrolled in the BH-VPN program that have an encounter with a self-harm code within 45 days of their ED visit
- Count/frequency of patients enrolled in the BH-VPN program that have an acute care visit (ED, IP, OBS) within 45 days of their ED visit
- Count/frequency of patients enrolled in the BH-VPN program that return to an Atrium Health emergency department with a telepsychiatric consult within 45 days of their ED visit

PHQ-9 are taken about every 2 weeks during a patient's enrollment. The post PHQ-9 score will be the score closest to the 45-day follow-up period.

- Count/frequency of patients enrolled in the BH-VPN program that improve their PHQ-9 score, among patients with an initial score >10
- Count/frequency of patients enrolled in the BH-VPN program that report suicide ideation on their initial PHQ-9 ($Q9>0$), that no longer report suicide ideation on their last PHQ-9 ($Q9=0$)
- Count/frequency of patients enrolled in the BH-VPN program with successful case closure (complete the 45-day follow-up period or have a successful referral in care)

5.2. Randomization and Allocation

Randomization will be based on days the navigators are available to treat patients who've completed their telepsychiatric consult. Patients may be in the ED for multiple days. Their enrollment status depends on the day and time of their initial telepsychiatric consultation. Navigation will only be available for those patients whose consult occurs during intervention day/times. As part of the research design and rollout of this project, randomization will occur at the day level with the days being identified as intervention or usual care days for the duration of the study. Patients will accrue in both arms of the study during the navigators' days and hours of operation. Patients will not be accrued on days where the navigators are not potentially available such as weekends, nights, and holidays.

Block randomization will be used to assign days the intervention is offered. In each 7-day period (Monday through Saturday) there will be three days the program is offered and three days where the program is not offered. The program is not available to patients in the ED on Sundays. The hours of availability are 7AM to 11PM Monday through Friday and 7AM to 7PM on Saturdays.

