3. RATIONALE

To enhance the care of patients with a telepsychiatric consult, Atrium Health has designed a Behavioral Health Virtual Patient Navigation (BH-VPN) program. Navigators will monitor patients and assist with navigation through a weekly phone call after their index ED encounter for up to 45 days post ED discharge. The BH-VPN aims to improve patient outcomes through standardized approaches that leverage analytics and technology, while bridging care coordination. When a patient presents to a participating Atrium Health ED, those with a telepsychiatric consult completed on a randomized intervention day, during the hours of operation, are provided the option of participating in the BH-VPN program. A patient can choose not to receive care by a navigator post discharge.

The BH-VPN program includes the following key components: introduction to the patient follow-up process prior to ED discharge, follow-up evaluation within 72 hours by phone and weekly contact, confirmation that a follow-up visit is scheduled, where applicable confirm in-network follow-up appointments are completed with an Atrium Health provider, and placement into an appropriate case management program, if needed. There may be cases where patients are eligible to enroll in full case management programs based on their insurance and other criteria. For example, if a patient has Medicaid through Cardinal Innovations, a managed care organization providing local behavioral health care, and meets specific criteria, would no longer require navigation services. A patient's contact with the BH-VPN program ends after 45 days following ED discharge, or if there is a failure to contact, becomes enrolled with a case-management program, declines services, or the patient dies. For those patients enrolled in a case management program, then navigator will ensure the patient is in contact with case management program staff before ending contact with the patient.

This research project is a pragmatic, randomized evaluation of a quality improvement initiative which seeks to evaluate the effects of standardizing the use of a BH-VPN program among patients with a telepsychiatric consult. The outcomes evaluation of this intervention has been designed to integrate with routine care and minimize frontline staff burden by deploying an evaluation in a real-world setting.

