5.3. Behavioral Health Virtual Patient Navigation (BH-VPN) Program

The BH-VPN outlines the flow of patients from initial contact to their follow-up calls (see Appendix 1). In the existing ED workflow, patients are identified by a clinician in the ED as needing psychiatric evaluation and a referral is made to a tele-psych provider for a virtual consult. Patients who complete a telepsychiatric consult in the ED can be enrolled to either the control or intervention arm based on a randomization scheme that randomly allocates days that navigators are available. Psychiatrists are reminded through daily communication as to whether the BH-VPN program is available and the ED locations. The psychiatrist will make a recommendation to admit or discharge the patient. The ED physician will make the final decision on whether to admit or discharge the patient from the ED. Patients that have a discharge recommendation on days the program is available, will be offered the BH-VPN program. Enrolled patients are followed for up to 45 days.

If a discharge recommendation is made, a patient will be approached again by the navigator virtually for enrollment into the BH-VPN program. The patient has the option not to be followed by the navigator. Before discharge, the navigator will complete an initial virtual behavioral health assessment. The initial health assessment contains information such as preferred communication method, primary care provider, psychiatry provider, PHQ-9 screening, collateral resources, recent ED and hospital utilization, substance use disorder, medication barriers, appointment barriers, community resources, and crisis planning.

The follow-up assessments, which will occur during navigation phone calls at least weekly, may include information such as a suicide ideation safety screening, an appointment reminder, appointment barrier evaluations, medication obtainment follow-up, substance use disorder follow-up, PHQ-9 screening, supportive listening, psychoeducation, community resource follow-up, and additional crisis planning. Phone calls are weekly as standard care but may be more often depending on the individual needs of the patient. Appointments are dependent on a patient's specific needs and may be with a therapist or psychiatrist as well as other providers in the community such as primary care or referral to a community provider.

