8.1. Protocol and Pathway Training

Background, protocol and process steps will be presented to psychiatrists and nurse practitioners who will be providing virtual psychiatric consultations. The role of virtual patient navigator and randomization scheme will be presented so expectations are clear that this is not available every day/time or weekends. This will be presented at the Department of Psychiatry meeting, which includes Emergency and Telepsychiatry Departments. Attendees may also include providers, who at some point may see patients who have been through this pathway but will not be directly involved in providing evaluations. Education will be provided to the emergency department staff involved in this project, so that they are aware of the process and the role of the virtual patient navigator.

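### A patient's arm is set by the day of the first completed consult, after that day's status is known, and the plan does not measure whether consult timing differs by arm

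*Combined protocol and SAP*

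**What the plan says.** Section 5.2 makes the calendar day the randomized unit: "randomization will occur at the day level with the days being identified as intervention or usual care days". Each Monday-to-Saturday week has three program days and three usual-care days. The patient's own arm follows a later event: "Their enrollment status depends on the day and time of their initial telepsychiatric consultation". Section 3 describes the program as offered to "those with a telepsychiatric consult completed on a randomized intervention day, during the hours of operation", so completion of the consult is what counts. Section 5.2 also notes: "Patients may be in the ED for multiple days".

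On who knows what, Section 5.3 states: "Psychiatrists are reminded through daily communication as to whether the BH-VPN program is available and the ED locations". The same section has the psychiatrist recommend admission or discharge, leaves the final decision to the ED physician, and offers navigation to patients with a discharge recommendation on program days. Under Section 8.1, the training "will be presented to psychiatrists and nurse practitioners who will be providing virtual psychiatric consultations", and "The role of virtual patient navigator and randomization scheme will be presented so expectations are clear" about when the program is unavailable.

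Some protections exist. Only the initial consult counts (5.2), each patient is analyzed once (4.3), and analysis is by intention to treat (6.2). The synopsis lists, among the foundation reporting items, counts of patients with a consult in both arms.

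**The concern.** Randomizing days protects the comparison only if the patients who fall on program days and usual-care days are alike apart from the program. Here the event that places a patient on a day occurs after the day's status has been announced to the people performing the consult. Navigation is offered only to patients recommended for discharge, so any reason to wait for a program day applies mainly to patients expected to go home.

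Moving such patients takes non-admissions out of usual care and adds them to the program arm. That produces the lower program-day admission rate that Section 1.1 predicts. The intention-to-treat rule in Section 6.2 gives no protection, because assignment is itself defined by consult timing. The baseline variables in Section 5.1.2 are age, race, gender and Charlson score. None of them measures likely psychiatric disposition, so the balance tests and covariate adjustment could miss the shift.

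**Working it through.** **Inputs.** From Section 6.1: 60% admission under usual care, target N of 1,133, ICC 0.1 with 2 patients per ED per day. From Section 6.2: two-sided tests. From Section 5.2: 3:3 weekly blocks. Assumed here: no true effect, an even split, and a fraction *f* of discharge-bound usual-care-day patients whose first consult moves to a program day. The documents give no value for *f*, so a range is shown.

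**The plan's own figure.** Design effect 1 + (2 − 1) × 0.1 = 1.1, and 1,030 × 1.1 = 1,133, as stated. The base of 1,030 does not reproduce: 60% v 52%, two-sided 0.05 and 85% power need 1,380. That is a separate matter. Here 1,133 is used only as the planned trial size.

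**False difference.** Each arm starts with 1,133 / 2 = 566.5 patients, of whom 0.40 × 566.5 = 226.6 are discharge-bound.
- Usual care: 0.60 / (1 − 0.40*f*)
- BH-VPN: 0.60 / (1 + 0.40*f*)

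The false-positive rate is the rejection probability of a two-sided pooled z test, with each arm's size divided by 1.1.

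| *f* | Patients moved | Usual care | BH-VPN | Difference | False positives |
|---|---|---|---|---|---|
| 0 | 0 | 60.0% | 60.0% | 0 | 5% |
| 5% | 0.05 × 226.6 ≈ 11 | 0.60/0.98 = 61.2% | 0.60/1.02 = 58.8% | 2.4 points | about 12% |
| 10% | 0.10 × 226.6 ≈ 23 | 0.60/0.96 = 62.5% | 0.60/1.04 = 57.7% | 4.8 points | about 35% |

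With base admission rates of 50%, 60% and 70%, *f* = 10% gives 5.0, 4.8 and 4.2 points.

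**How much the block reveals.** A 3:3 block has 20 orderings and 20 × 3 = 60 usual-care days. The next day is certain to be a program day only after the third usual-care day, and only if that day is not the sixth. The third usual-care day falls on day 3, 4, 5 or 6 in 1, 3, 6 or 10 orderings. So 1 + 3 + 6 = 10 of 60 usual-care days, or 1 in 6, have a next day certain to be a program day.

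Suppose holding occurred only under that certainty, with patients spread evenly over days. Then *f* = 5% means holding 5 / 16.7 = 30% of discharge-bound patients on those days, and *f* = 10% means 60%. Acting on a guess is also possible: after a Monday-to-Friday usual-care day, the next day is a program day 60% of the time.

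**Would the planned counts show it?** At *f* = 10% the arms hold about 544 and 589 patients. z = (589 − 544) / √1,133 = 45 / 33.7 ≈ 1.3, which looks like chance.

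**Consults pushed past closing.** A short delay beyond 11PM does not change a patient's arm; it removes the patient from accrual. Losing 10% of discharge-bound usual-care-day patients in this way gives 62.5% v 60%, a false difference of 2.5 points.

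**The case against.** The case against is substantial, and much of it stands.

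- **Control of timing.** A reader might infer that psychiatrists decide when the consult happens. No section says so. An ED clinician identifies the patient and makes the referral, and scheduling is not described.
- **Block structure.** A reader might infer that clinicians are taught the 3:3 block. Section 8.1 mentions only the randomization scheme, and its stated purpose is to explain that the program is not always available. Whether the block or future days are disclosed is not stated.
- **Sorting before evaluation.** Because the first consult fixes the arm, likely disposition would have to be guessed before the psychiatric evaluation. This makes selective holding harder. It does not rule it out, since an ED clinician has already seen the patient.
- **Length of the hold.** Changing arm requires at least the 11PM-to-7AM gap. The remark about multi-day stays does not show that first consults wait for days.
- **Large distortions.** A reader might infer that the full 8-point design difference could easily be manufactured. It needs *f* of about 16.6% (about 38 patients). With holding only under certainty, that means nearly every discharge-bound patient on the relevant days (16.6 / 16.7). Nothing in the documents supports that.
- **Existing checks.** Counts in both arms are planned, baseline characteristics are compared, and Section 9.2 has the team review enrollment and data integrity. It would be wrong to say there is no check. These checks are weak for this purpose, and arrival-to-consult time is not among them.

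Same-day awareness of availability is part of the intervention and cannot be blinded. What remains is that the plan could not readily tell whether selective timing had occurred.

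**Conclusion.** The point holds as a vulnerability in how patients are assigned to arms, not as evidence that bias will occur. Arm depends on the timing of an event that follows disclosure of the day's status, and intention-to-treat by that same event cannot correct for selective timing. Under the stated assumptions, moving about 11 patients raises the false-positive rate from 5% to about 12%, and moving about 23 raises it to about 35%. These figures rest on an assumed fraction and on movement that is entirely one-way and confined to discharge-bound patients. A shift unrelated to likely disposition would give no bias. The change is worth making because it costs little and supplies evidence that the current plan would not produce.

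**What to change.** Keep consult-day assignment as the main analysis, and make three additions.

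1. **Section 6.2:** prespecify a sensitivity analysis of the primary outcome in which arm is the status of the first operating window open at or after ED arrival, taken from the EHR time stamp. Section 5.2 excludes weekends yet gives Saturday hours; reconcile this so that the operating window is unambiguous.
2. **Reporting:** alongside the consult counts already listed in the synopsis, report by arm the arrival-to-consult time and the share of consults completed on a later day than arrival. State in advance that an imbalance limits the causal reading.
3. **Section 8.1:** tell clinicians that availability varies by day, without giving the block structure or the status of future days.

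The cost is some plan wording, one EHR time stamp and one extra model run. The arrival-based estimate has limits. It is diluted where the arrival window and the consult day differ in status, so a null result would not by itself separate dilution from selective timing. It also cannot recover patients whose consult fell outside operating hours. It should be labeled supportive.

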6.2. Statistical analysis

Prior to analysis, descriptive statistics will be calculated to screen all variables for accuracy and to examine distributions.

All analyses will follow the intention-to-treat (“ITT”) principle, such that patients will be analyzed based on their assignment to the BH-VPN program or usual care. Balance in baseline characteristics between the groups will be assessed using Student’s t-test for normally distributed data, the Wilcoxon rank sum test for ordinal data or interval data that are not normally distributed, and the chi-square test for categorical data. Normality will be assessed using the Shapiro Wilk test and Q-Q plots.

The primary outcome, hospital admission (yes/no), is a binary dependent variable and will be compared between the BH-VPN and usual care groups using a generalized linear mixed-effects model with a logit link function. To adjust for correlation among patients seen on the same day and in the same ED, the model will include a random effect term for day nested within ED. The primary predictor in the model is an indicator for assignment to the BH-VPN program versus usual care. Additional baseline covariates will be included in the model if they are either strongly correlated with the dependent variable or show baseline imbalance between the two groups.

A similar approach will be used for the secondary outcomes to assess the patient-centric 45-day utilization rate, encounters with a self-harm diagnosis rate, and ED readmission rate. The models assessing these measures will be generalized linear mixed-effects models with a logit link, where utilization, diagnosis, or readmission, (yes/no) is the binary dependent variable. Independent variables in the models will be as described above for the primary analysis.

In addition, per-protocol analyses of the primary and secondary outcomes will be performed to evaluate the effect of BH-VPN program participation, in contrast to the ITT analysis evaluating the effectiveness of randomization to the program. The per-protocol analyses will include only subjects who received and adhered to the treatment (BH-VPN program or usual care).

Other binary outcome variables (e.g., frequency of patients active in the BH-VPN program) will be analyzed using descriptive statistics, unadjusted odds ratios, and 95% confidence intervals.

All tests will be two sided and the data will be analyzed using SAS Enterprise Guide 7.1 (SAS Institute Inc., Cary, NC, USA).

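### Days are randomised 3:3 within weekly blocks, but the Section 6.2 models omit the week block and day of week: a modest loss of precision, not bias

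*Combined protocol and SAP*

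**What the plan says.** Section 5.2 makes the calendar day the unit of randomisation: "randomization will occur at the day level with the days being identified as intervention or usual care days". On the method it says: "Block randomization will be used to assign days the intervention is offered". Each week forms one block, restricted as follows: "In each 7-day period (Monday through Saturday) there will be three days the program is offered and three days where the program is not offered". Saturday has a different accrual window from the other days: "The hours of availability are 7AM to 11PM Monday through Friday and 7AM to 7PM on Saturdays". That is 16 hours Monday to Friday and 12 hours on Saturday.

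Section 6.2 specifies a logit mixed model. For clustering, "the model will include a random effect term for day nested within ED". On fixed effects, "The primary predictor in the model is an indicator for assignment to the BH-VPN program versus usual care". Anything further depends on a screen: "Additional baseline covariates will be included in the model if they are either strongly correlated with the dependent variable or show baseline imbalance". Secondary outcomes use the same independent variables. The baseline variables named in Section 5.1.2 are age, race, gender and the Charlson score. Neither week, calendar time nor day of week is named as a model term anywhere.

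**The concern.** Blocking by week balances the arms over calendar time, during an accrual of about 14 months (Section 4.1). A model with no week or calendar term does not use that balance. Week-to-week variation in admission rates falls into the day-within-ED variance and is treated as noise in the arm comparison, although the 3:3 split has largely cancelled it.

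The covariate screen does not reliably close the gap. Week is balanced by design, so the imbalance route would rarely select it. Whether anyone would test it for correlation with the outcome is left open.

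Day of week is a separate matter. The block does not balance it, and Saturday differs at least in hours. A chance excess of program Saturdays would add noise to the estimate. At stake is power in a trial whose expected accrual (about 1,100) is already a little below its target (1,133).

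**Working it through.** **Inputs from the documents.** 60% admission under usual care and an 8-point reduction, so 52%; total 1,030, design effect 1.1, target 1,133, ICC 0.1 (Section 6.1). Two-sided tests (Section 6.2). About 1,100 patients in 14 months (Section 4.1). Six randomised days per week, split 3:3 (Section 5.2).

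**Assumptions, because the documents give no figure.** Day-to-day logit SD 0.3; week-to-week logit SD 0, 0.3, 0.6 or 1.0; a 12-point Saturday difference in admission rate; consults proportional to opening hours.

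**1. The plan's own figures.** The inflation reproduces: 1 + (2 − 1) × 0.1 = 1.1, and 1,030 × 1.1 = 1,133. The stated 85% power does not. With 515 per arm and pooled rate 0.56, z = [0.08 × √515 − 1.96 × √(2 × 0.56 × 0.44)] / √(0.24 + 0.2496) = (1.816 − 1.376) / 0.700 = 0.63, which is 73.5% power. That is a separate matter, noted here because it explains why the power figures below start near 0.74.

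**2. Why omitting week widens the standard error.** 14 months is 14 × 365.25 / 12 / 7 = 60.9 weeks, taken as 61 weeks or 366 days, with 1,133 / 366 = 3.1 patients per day. On the probability scale a logit SD s is roughly 0.24 × s. The variance of a day's admission proportion around its week is 0.24 / 3.1 + (0.24 × 0.3)² = 0.0775 + 0.0052 = 0.0827. A model without week uses this plus (0.24 × week SD)²:

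- Week SD 0.3: 0.0879 / 0.0827 = 1.063; standard error too large by √1.063 = 1.03; true two-sided level about 0.043.
- Week SD 0.6: 0.1034 / 0.0827 = 1.25; standard error too large by 1.12; true level about 0.028.

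**3. Simulation.** 61 weeks of six days, permuted 3:3 within week, mean total 1,133, 1,500 trials per setting; weighted day-level analysis of the risk difference, without week and with week as a fixed factor, on the same simulated trials.

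| Week SD | Null rejection, no week | Null rejection, week | Power, no week | Power, week |
|---|---|---|---|---|
| 0 | 0.051 | 0.053 | 0.74 | 0.73 |
| 0.3 | 0.048 | 0.053 | 0.70 | 0.71 |
| 0.6 | 0.033 | 0.051 | 0.60 | 0.67 |
| 1.0 | 0.029 | 0.059 | 0.45 | 0.63 |

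Simulation error is about ±0.011 for null rejection and ±0.025 for power. With weekday effects of up to ±0.3 on the logit scale, power without either term is 0.72, 0.67, 0.60 and 0.45; with week and day of week it is 0.70, 0.68, 0.66 and 0.64.

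A second, smaller run (250 trials per setting, so power is known only to about ±0.06) used a random week intercept and a Saturday term. Power without and with the terms was 0.74 and 0.73 at SD 0, 0.67 and 0.68 at SD 0.3, and 0.56 and 0.65 at SD 0.6. Null rejection at SD 0.6 was 0.024 and 0.04.

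At SD 0.6 the gains are therefore 7, 6 and 9 points.

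**4. Which week SDs are plausible.** Around 60%, the central 95% of weekly admission rates runs from about 45% to 73% at SD 0.3, 32% to 83% at 0.6 and 17% to 91% at 1.0. If the whole ICC of 0.1 in Section 6.1 were week variation on the latent logit scale, the SD would be √[(0.1 / 0.9) × π² / 3] = 0.60. So 0.6 is close to a ceiling under the plan's own ICC, and 1.0 lies outside it. The plan does not say on which scale its ICC is defined.

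**5. Saturday.** Over about 60 weeks the number of program Saturdays is Binomial(60, 0.5): mean 30, SD √15 = 3.9, 95% range about 22 to 38. A Saturday carries 12 / 16 = 0.75 of a weekday's patients. Each arm has 180 days.

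- 38:22 split: program share 28.5 / 170.5 = 16.7%; usual care 16.5 / 174.5 = 9.5%. The gap of 7.3 points × 0.12 = 0.9 points.
- 34:26 split (one SD): 25.5 / 171.5 = 14.9%; 19.5 / 173.5 = 11.2%. The gap of 3.6 points × 0.12 = 0.4 points.

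The standard error of the arm difference is √(0.4896 / 515) = 3.1 points. A one-SD Saturday shift is thus about (0.4 / 3.1)² = 2% of the variance.

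**The case against.** A reader might infer that the analysis ignores the groups by which the trial randomises. The documents do not support that. The randomised unit is the day, and Section 6.2 has a random effect for day within ED. What is missing is the restriction on the randomisation, the week. Day of week is not a randomisation factor at all.

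A reader might also infer bias or a raised false-positive rate. Neither follows. Leaving out a balanced block makes the test conservative, and chance weekday imbalance under random allocation is ordinary sampling variation that the standard error is meant to cover.

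The size is also open to challenge. At a week SD of 0.3 or less no gain can be told from simulation error. The 12-point Saturday difference has no source in the documents, and 38:22 is the edge of the range. The simulations use a day-level linear model with no ED level, not the planned mixed model. Finally, the covariate rule in Section 6.2 is not limited to patient-level variables, so it could admit day of week.

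All of this stands, and it limits the point to a precision refinement. It does not remove it: the covariate rule guarantees neither term, both are known in advance, and the cost of including them is very small.

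**Conclusion.** The point holds as a minor one. Section 5.2 blocks by week, and Section 6.2 specifies neither week nor calendar time. If weeks differ, the standard error is too large and power is lost. The loss is negligible at a week-to-week logit SD of 0.3 or less and, allowing for the small second run, about 6 to 10 points at 0.6. The larger loss at SD 1.0 (about 18 points) should not be relied on, since it needs more variation than the plan's own ICC allows. Weekday imbalance adds a little noise: under the assumed 12-point Saturday difference, about 0.4 points at one SD and 0.9 at the edge of the range, against an 8-point target. All of these sizes rest on assumed variances and a simplified model; the direction does not.

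**What to change.** In Section 6.2, add to the primary and secondary models (i) a random intercept for randomisation week and (ii) a fixed Saturday indicator, or day of week. Derive both from the date of the initial telepsychiatric consult, which Section 5.2 already uses to set the arm, and exempt both from the covariate screen. A random intercept is preferable to about 60 fixed week terms in a logistic model with roughly 18 patients a week. If the sponsor prefers to leave the terms out, the SAP should say why.

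Section 5.2 should also be reconciled with itself: it gives Saturday hours and counts Saturday among the six randomised days, yet lists weekends among the times when patients are not accrued. The Saturday term presumes that Saturdays count.

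The cost is one sentence and no new data. If weeks and weekdays do not in fact differ, the terms cost at most about 1 to 2 points of power.
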